3.1 Overall Study Design and Plan

This will be a double-masked, randomized, multicenter, placebo-controlled, parallel-group efficacy and safety trial evaluating reduction of elevated IOP with netarsudil ophthalmic solution over a 28-day treatment period. The purpose of this study is to assess the efficacy and safety of netarsudil ophthalmic solution (0.01%, 0.02% and 0.04%) compared to placebo in subjects that are 20 years of age or older with OAG or OHT in Japan.

All investigational products will be dosed in both eyes (OU) QD in the evening (PM). Subjects eligible to be enrolled in this study will be those with a diagnosis of either OAG or OHT. Approximately 208 subjects will be enrolled. Subjects who agree to participate in this study and are enrolled in the study will attend a total of 6 study visits: Screening Visit, Qualification Visit #1, Qualification Visit #2/Day 1 (baseline), Week 1 (Day 8), Week 2 (Day 15), and Week 4 (Day 29).

Subjects will be required to washout of their pre-study ocular hypotensive medication for a prescribed period (i.e., 5 days to at least 6 weeks, depending on the medication) prior to attending Qualification Visit #1. Subjects eligible to be enrolled in this study must meet all inclusion criteria and none of the exclusion criteria at each of the Screening Visit and Qualification Visits #1 and #2. Subjects will receive a baseline eye examination including IOP measurements at the Screening Visit and Qualification Visits #1 and #2, and undergo additional testing at Qualification Visit #2 including VFQ-25, BCVA, and CS testing. If deemed eligible, the subject will be enrolled at Qualification Visit #2 and assigned to placebo or 1 of 3 investigational products in a 1:1:1:1 ratio according to a computer-generated randomization list. Randomization will take place using IWRS methodology and will stratify subjects by site.

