4.3 Exclusion Criteria

Subjects meeting any of the following criteria during screening or qualification evaluations (e.g., at the time of randomization) will be excluded from entry into the study:

Ophthalmic:

1. Clinically significant ocular disease (e.g., corneal edema, uveitis, or severe keratoconjunctivitis sicca) which might interfere with interpretation of the study efficacy endpoints or with safety assessments, including subjects with glaucomatous damage so severe that washout of ocular hypotensive medications for up to 8 weeks is not judged safe as it would put the subject at risk for further vision loss
2. Pseudoexfoliation or pigment dispersion component glaucoma, history of angle closure glaucoma, or narrow angles (i.e., Shaffer Grade 2 or less). Note: Previous laser peripheral iridotomy is NOT acceptable
3. Ocular hyperemia score of moderate (+ 2) or severe (+3) at Qualification Visit #2
4. Previous glaucoma intraocular surgery, including selective laser trabeculoplasty (SLT) or argon laser trabeculoplasty (ALT) in the study eye
5. Refractive surgery in either eye (e.g., radial keratotomy, photorefractive keratectomy [PRK], laser-assisted in situ keratomileusis [LASIK], corneal cross-linking)
6. Ocular trauma within the 6 months prior to screening, or ocular surgery or non-refractive laser treatment within the 3 months prior to screening
7. Recent or current evidence of ocular infection or inflammation in either eye. Current evidence of clinically significant blepharitis, conjunctivitis, keratitis, or a history of herpes simplex or zoster keratitis in either eye at screening
8. Any corneal disease or condition in the either eye that in the investigator opinion, may confound assessment of the cornea
9. Current evidence of corneal deposits or cornea verticillata in either eye
10. Use of ocular medication in either eye of any kind within 30 days of screening and throughout the study, with the exception of a) ocular hypotensive medications (which must be washed out according to the provided schedule), b) lid scrubs (which may be used prior to, but not after, screening), c) lubricating drops for dry eye (which may be used throughout the study), or d) non-steroid allergy drops (note: must not contain a vasoconstrictor) as prescribed by the Investigator
11. Mean central corneal thickness greater than 620 μm in either eye at screening

12. Any abnormality preventing reliable applanation tonometry of either eye (e.g., keratoconus)

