13. Known hypersensitivity to benzalkonium chloride or excipients of netarsudil ophthalmic solution
14. Cannot demonstrate proper delivery of the eye drop, or, in the principal investigator or co-investigator's opinion, unable to deliver the eye drop consistently

Systemic:

15. Current use of systemic medications known to cause corneal deposits or cornea verticillata including nonsteroidal anti-inflammatory drugs (NSAIDs), amiodarone, chlorpromazine, hydroxychloroquine, tamoxifen and phenothiazines
16. Clinically significant abnormalities in laboratory tests at screening
17. Clinically significant systemic disease which might interfere with the study
18. Participation in any investigational study within 30 days prior to screening
19. Systemic medication that could have a substantial effect on IOP within 30 days prior to screening, or anticipated during the study, including any corticosteroid-containing drug regardless of route of administration
20. Women of childbearing potential who are pregnant, nursing, planning a pregnancy, or not using a medically acceptable form of birth control. Acceptable birth control includes: condoms plus intrauterine devices or condoms plus oral hormonal contraceptives, double barrier methods (e.g., condoms with spermicidal gel plus diaphragms). Birth control must be continued for at least 30 days after the last dose of the study drug. An adult woman is considered to be of childbearing potential unless she is 1 year post-menopausal or 3 months post-surgical sterilization. All females of childbearing potential must have a negative urine pregnancy test result at the screening examination and must not intend to become pregnant during the study

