5.7 Restrictions

5.7.1 Prior Therapy/Washout Period

Subjects currently using ocular hypotensive medications must undergo a minimum washout period as specified in Table 1.

If washout is to be extended beyond 8 weeks (56 days) for logistical or other reasons, the Sponsor should be contacted.

Table 1 Ocular Hypotensive Medication Washout Period

Medication Class	Minimum Washout Period
Rho kinase inhibitor	6 weeks
Prostaglandins	4 weeks
β -adrenoceptor antagonists	4 weeks
Adrenergic agonists (including α -agonists such as brimonidine and apraclonidine)	2 weeks
Muscarinic agonists (e.g., pilocarpine), carbonic anhydrase inhibitors (topical or oral)	5 days

[Hughes 2005](#)

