6.10.3 Pregnancy testing (for women of child bearing potential)

A urine human chorionic gonadotropin (hCG) pregnancy test (only for females who are not diagnosed as postmenopausal or surgically sterile) will be used in this study and performed at the screening visit to immediately confirm non-pregnancy eligibility for females of child-bearing potential.

The Sponsor will provide urine pregnancy tests to the sites. Expiration dates on the pregnancy tests will be reviewed and confirmed by the site prior to use.

If a female becomes pregnant during the study, the Investigator should notify the Sponsor immediately after the pregnancy is confirmed and the subject will be exited from the study. The Investigator should follow the progress of the pregnancy until the fetus is carried to term.

If the female partner of a subject become pregnant, the Investigator should collect information on the outcome of the pregnancy and the health of the baby (if applicable). The information will be reported to the sponsor to be used to understand the safety of the drug used during pregnancy.

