- A non-dilated eye examination will be performed, including IOP measurements and biomicroscopy. IOP must be measured between 09:00 and 09:30 hours.

Any new or worsening of symptoms beyond those collected at baseline are to be entered as AEs.

Subjects are allowed to leave the Investigator’s office between assessments and eat and drink without restrictions. However, subjects are not to consume alcohol or engage in strenuous exercise.

7.3.8 Visit 5.1 (Week 2 [Day 15], for IOP and safety measurements at 11:00 hours)

Subjects will be examined, and each examination will include:

- Symptomatology: Individuals will be asked “How are you feeling?”

- Recording of any AEs
- A non-dilated eye examination will be performed, including IOP measurements and biomicroscopy. IOP must be measured between 11:00 to 11:30 hours.

Subjects are allowed to leave the Investigator's office between assessments and eat and drink without restrictions. However, subjects are not to consume alcohol or engage in strenuous exercise.

7.3.9 Visit 5.2 (Week 2 [Day 15], for IOP and safety measurements at 16:00 hours)

Subjects will be examined, and each examination will include:

- Symptomatology: Individuals will be asked "How are you feeling?"
- Recording of any AEs
- A non-dilated eye examination will be performed, including IOP measurements and biomicroscopy. IOP must be measured between 15:30 and 16:30 hours.

Subjects will be:

- Instructed to continue to administer their masked medication at home between 20:00 - 22:00 hours (taking the daily evening dose on that day)
- Instructed to return to the office with their study medication on Week 4 (Day 29)

7.3.10 Visit 6.0 (Week 4 [Day 29], for IOP and safety measurements at 09:00 hours)

Subjects will return to the Investigator's office. The subject will be questioned about any missed doses and any changes in their health or concomitant medication use. Subjects will be examined, and each examination will include:

- Heart rate and blood pressure
- Symptomatology: Individuals will be asked "How are you feeling?"
- Recording of any AEs
- Urine pregnancy test (tests for applicable female subjects of child bearing potential may be performed at any time point throughout Visit 6)
- Blood samples will be taken for clinical chemistry and hematology, and a urine sample will be taken for urinalysis (samples may be taken at any time point throughout Visit 6)
- BCVA

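### The pregnancy exclusion applies through randomization, but the only scheduled pre-dose test is at screening, a few days to about 10 or 11 weeks before the first dose

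*Protocol*

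**What the plan says.** On when the exclusions apply, Section 3.1 says that eligible subjects "must meet all inclusion criteria and none of the exclusion criteria at each of the Screening Visit and Qualification Visits #1 and #2". Section 4.3 opens: "Subjects meeting any of the following criteria during screening or qualification evaluations (e.g., at the time of randomization) will be excluded". Criterion 20 lists pregnancy among these exclusions. It also excludes women who are nursing, planning a pregnancy or not using an acceptable form of contraception.

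On when pregnancy is tested, criterion 20 requires that women of childbearing potential "must have a negative urine pregnancy test result at the screening examination". Section 6.10.3 says the urine test is "performed at the screening visit to immediately confirm non-pregnancy eligibility for females of child-bearing potential". Section 7.1 lists it at Visit 1. Sections 7.2 and 7.3.1 to 7.3.3 (Visits 2 and 3.0 to 3.2) do not list it, and at a re-qualification visit only IOP must be re-measured. The next scheduled test is in Section 7.3.10, where "tests for applicable female subjects of child bearing potential may be performed at any time point throughout Visit 6". Appendix 1 agrees: the pregnancy-test row is marked at Visit 1 and Visit 6.0 only.

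On what lies between, Section 5.7.1 and Table 1 set minimum washouts from 5 days to 6 weeks by drug class. The sponsor is to be contacted "If washout is to be extended beyond 8 weeks (56 days) for logistical or other reasons". Section 7.3.3 has the drug dispensed at Visit 3.2, with the first dose that evening.

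**The concern.** The clause that excludes pregnant women has no time limit of its own, and two sections extend the exclusions to randomization. The evidence for it is collected once, before washout begins. The screening IOP of a treated subject is a medicated value, so washout necessarily falls between the test and the first dose.

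A woman who conceives in that interval could be randomized with a valid negative screening result on file. Unless she recognizes and reports the pregnancy, or leaves treatment early, the next scheduled test comes after about 28 evening doses. Section 6.10.3 says that a subject who becomes pregnant is exited from the study, and Section 6.8.8 requires the pregnancy to be reported and followed to outcome. The stake is avoidable exposure during pregnancy. No effect on the efficacy analysis is claimed.

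**Working it through.** The documents give no figure for the interval from test to first dose, so there is none to reproduce. It follows from the visit rules.

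Inputs:
- Washout W, from Table 1: 5 days (muscarinic agonists, carbonic anhydrase inhibitors), 14 (adrenergic agonists), 28 (prostaglandins, beta-blockers), 42 (Rho kinase inhibitors). W = 0 if no washout is needed, since treatment-naive subjects are eligible (Section 4.2, criterion 3). W = 56 is the length beyond which the sponsor is contacted.
- Visit 2 to Visit 3: 2 to 7 days (Section 7.2).
- Re-qualification: up to 1 week after failing Visit 2 and up to 1 week after failing Visit 3 (Sections 7.2 and 7.3.1).
- First dose: evening of Visit 3.

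Formula: days from screening test to first dose = W + (2 to 7) + (0, 7 or 14).

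| Washout | W | Minimum, W + 2 | No re-qualification, W + 7 | One re-qualification week, W + 14 | Two weeks, W + 21 |
|---|---|---|---|---|---|
| None | 0 | 2 | 7 | 14 | 21 |
| Muscarinic agonist or carbonic anhydrase inhibitor | 5 | 7 | 12 | 19 | 26 |
| Adrenergic agonist | 14 | 16 | 21 | 28 | 35 |
| Prostaglandin or beta-blocker | 28 | 30 | 35 | 42 | 49 |
| Rho kinase inhibitor | 42 | 44 | 49 | 56 | 63 |
| 56-day washout | 56 | 58 | 63 | 70 | 77 |

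Three points on reading the table:
- The 2-day minimum assumes that Visit 2 directly follows screening. Laboratory results must be reviewed before Visit 2, or before Visit 3 if drawn at Visit 2, so a few days is more realistic.
- The maximum depends on interpretation. Criteria 4 and 5 require the two qualification visits to be 2 to 7 days apart. If that also binds a repeated Visit 3, the second re-qualification week drops out and the maximum is 56 + 7 + 7 = 70 days (10 weeks). Otherwise it is 56 + 7 + 7 + 7 = 77 days (11 weeks).
- Neither figure is a hard cap, because washout may run past 56 days after sponsor contact.

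Visit 6 is nominally 28 days after Visit 3. For a subject who completes treatment, the two tests are therefore 2 + 28 = 30 to 77 + 28 = 105 days apart, give or take the 3-day window at Visit 6.

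**The case against.** The strongest reply is that the protocol is consistent. Section 3.1 says that no exclusion may be met at each visit; it does not say that every confirmatory test must be repeated. Criterion 20, Sections 6.10.3 and 7.1 and Appendix 1 all place the test at screening. Corneal thickness (criterion 11) and laboratory abnormalities (criterion 16) are likewise judged at screening. Part of this stands: the documents do not show a flat contradiction. But criteria 11 and 16 are limited to screening by their own wording, whereas in criterion 20 only the test is so limited, not the exclusion of pregnant women.

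A second reply is that safeguards exist. Criteria are reviewed again at Visits 2 and 3.0 to 3.2, changes in health are asked about at Visits 2 and 3.0, and contraception is required. These reduce the risk, but none supplies a new test result, and a subject may not know of an early pregnancy.

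A reader might also infer three stronger points that the documents do not support:
- *Every subject has a gap of at least 4 weeks.* That floor holds only for prostaglandin, beta-blocker or Rho kinase inhibitor washouts, or for a washout of similar length. With no washout or a shorter one, the minimum is about 2, 7 or 16 days.
- *The exclusion cannot be verified at Visit 3.* It is reviewed there; what is missing is a scheduled test.
- *Any such pregnancy is found only after a full course.* Early discontinuation, or cornea verticillata at Visit 4 or 5, brings the Visit 6 procedures forward, including the urine test.

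**Conclusion.** The concern holds as a gap between where the exclusion applies and where it is tested. For every woman of childbearing potential, no scheduled test confirms non-pregnancy when drug is dispensed. The interval since the screening test varies widely with prior medication and is longest after the longer washouts and re-qualification.

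The number of women exposed to this gap cannot be computed, because the documents give neither the share of childbearing potential nor the share in each washout class. The results of the reproductive toxicity studies are not in these documents either, so the size of the harm is not estimated.

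One caveat concerns versions. The SAP Introduction cites protocol Amendment 2, whereas the protocol reviewed is Amendment 1. The SAP's visit schedule appears unchanged on this point, but its columns are not fully legible. With those limits, this is a modest patient-safety improvement that the sponsor should make.

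**What to change.** Reconcile Sections 3.1 and 4.3, under which the exclusion applies through randomization, with criterion 20, Section 6.10.3 and Appendix 1, which place the only pre-dose test at screening. The protocol should state explicitly how the pregnancy exclusion is verified at the visit where drug is dispensed. Whether and when to test is the sponsor's clinical decision. Check the current amendment first, and keep the SAP's Table 3-1 in line with the result.

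The textual change costs little. If the sponsor decides on further testing, urine kits are already supplied to sites (Section 6.10.3) and Visit 3 already runs from 09:00 to 16:00. The downside would be a small added burden for women of childbearing potential and an occasional late screen failure.

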5. STUDY TREATMENTS

5.1 Description of Treatments

5.1.1 Study Drug

Netarsudil mesylate (AR-13324) Ophthalmic Solution is a sterile, isotonic, buffered aqueous solution containing netarsudil (0.01%, 0.02% or 0.04%), boric acid, mannitol, water for injection, and preserved with benzalkonium chloride (0.015%). The product formulations are adjusted to approximately pH 5.

5.1.2 Placebo or Control Drug

Netarsudil ophthalmic solution placebo is a sterile, isotonic, buffered aqueous solution containing boric acid, mannitol, water for injection, and preserved with benzalkonium chloride (0.015%). The product formulations are adjusted to approximately pH 5.

5.2 Treatments Administered

Subjects will be randomized to receive IP netarsudil ophthalmic solution (0.01%, 0.02% or 0.04%) or its placebo administered OU. Subjects will instill 1 drop into each eye QD in the evening between 20:00 and 22:00 hours. IP doses will be administered by the study subjects. For subjects deemed unable to self-administer the doses, a guardian or alternative caregiver will be asked to administer the medication. All subjects will administer study treatment for approximately 28 days.

5.3 Selection and Timing of Dose for Each Patient

The study drug doses and treatment period selected for this study are based on one Phase 1 study ([AR-13324-CS101](#)) and the positive outcomes seen for netarsudil in 2 previously completed Phase 2 studies ([AR-13324-CS201](#) and [AR-13324-CS202](#)) and 4 completed Phase 3 studies ([AR-13324-CS301](#), [AR-13324-CS302](#), [AR-13324-CS303](#) and [AR-13324-CS304](#)). Each dose is being administered QD OU in the evening (between 20:00 and 22:00 hours) in this study, since this dosing regimen was found to provide good efficacy and tolerability in the previous clinical studies.

5.4 Method of Assigning Patients to Treatment Groups

A randomization code for allocating the treatments will be prepared by an independent biostatistician who is not involved in the day-to-day conduct of the study. Subjects will be randomized using IWRS in a 1:1:1:1 ratio to receive netarsudil ophthalmic solution (0.01%, 0.02% or 0.04%) or its placebo and will stratify subjects by site.

5.5 Masking

Treatment assignments will be masked to the Investigator, the clinical study team (Sponsor, personnel involved in day to day study management, Monitors, Data Managers, and Statisticians), and the subjects for the duration of the study. Only in case of medical emergency or occurrence of AEs that warrant unmasking in the opinion of the Investigator, will the treatment assignment(s) be unmasked and made available to the Investigator and the Sponsor Medical Monitor or designee. Individual unmasking by the Investigator will normally result in withdrawal of the subject from the study and should only be performed for the specific subject requiring unmasking in their treatment group. In the absence of medical need, the randomization code will not be available to the above personnel until after the study is completed and the database is unlocked.

If the Investigator feels it is necessary to unmask a subject's treatment assignment after an emergency situation, the Investigator should contact the Sponsor Medical Monitor or designee. After consultation with the Sponsor Medical Monitor or designee, a decision will be made as to whether or not the treatment should be unmasked. The treatment assignment will be revealed on a subject-by-subject basis, thus leaving the masking on the remaining subjects.

If there is an emergency situation in which treatment of an AE requires immediate unmasking, and the Investigator is unable to contact the Sponsor Medical Monitor or designee, the Investigator may unmask the treatment. The Investigator will perform the unmasking through the IWRS or other randomization system. In the case of such unmasking in an emergency situation, the Investigator should contact the Sponsor immediately and document unmasking in writing, recording the date, time, and reason for unmasking the study drug treatment in the source documentation.

5.6 Concomitant Therapy

As noted in Section 5.7.1, subjects using ocular hypotensive medications at screening are required to undergo a washout of their current ocular hypotensive medications. Intermittent use of over-the-counter (OTC) artificial tear lubricant products is acceptable, with a minimum of 10 minutes between OTC products and study medication.

Prohibited medications include concurrent therapy of:

- Any form of ocular hypotensive medications (prescription or OTC)
- Miotics
- Epinephrine-related compounds
- Carbonic anhydrase inhibitors
- α -adrenoceptor agonists

- β -adrenoceptor antagonists
- Muscarinic agonists (e.g., pilocarpine)
- Ocular prostaglandin analogues
- Rho kinase inhibitors
- Any corticosteroid containing ocular or systemic drug regardless of route of administration
- Systemic medications known to cause corneal deposits or cornea verticillata including nonsteroidal anti-inflammatory drugs (NSAIDs), amiodarone, chlorpromazine, hydroxychloroquine, tamoxifen and phenothiazines

Systemic therapy with agents other than corticosteroids that could have an effect on IOP is to be consistent in dose, regimen and agent within the 30 days prior to screening and throughout the study is allowed. For example, a subject can be treated with a systemic β -adrenoceptor antagonist as long as the particular agent and its dose and regimen had been consistent for the 30 days prior to screening, and there is no reason to believe that alteration would be necessary at some point later during the study. Subjects should be cautioned to avoid use of alcohol or the use of any drugs such as cannabis or marijuana during the study visit days.

Contact lens wear during the study is acceptable. However, subjects must remove their contact lenses at least 30 minutes before instillation of study medication, and not place them in their eye(s) until 30 minutes after instillation. Subjects will be informed that benzalkonium chloride contained in this study drug as preservative agent has a risk to distain contact lenses.

Use of all medications should be documented on the appropriate case report form (CRF). Investigators are encouraged to contact the Sponsor/Sponsor representative for any questions regarding allowed medications. Judgment of continued study participation by the subject, and inclusion of this subject's subsequent visits in the safety and efficacy analysis will be made by the Sponsor.

All medications which the subject has taken within 30 days prior to screening and during the study will be recorded in the CRF. The name of the drug, dose, route of administration, duration of treatment and indication will be recorded for each medication. For combination products (e.g., Contac[®]), the brand name is required. For non-combination products, the generic name is desired. The use of routine ophthalmic diagnostic pharmaceutical agents (e.g., fluorescein and local anesthetic) will be allowed, and individual documentation not required. Any change in dosing parameters should also be recorded in the CRF.

